16.2 Sample Size, Accrual Rate and Study Duration

For this feasibility study, the planned sample size is 24 patients (8 in cohorts 1 (1A and 1B)), 4 in cohort 2, and up to 12 in cohort 3 to enroll a maximum of 24 evaluable patients in the trial). The total sample size may need to be adjusted to allow for replacement of participants who withdraw prior to completion of the third week of chemoradiation, as these are the only reasons for replacement. It is anticipated that 4 patients will be enrolled per month for an approximate accrual period of 9 months. All patients who begin protocol therapy will be included in the evaluation of toxicity for 30 days post last treatment, unless patient withdraws from study.

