16.1.1. Safety review

A safety review for each cohort will be conducted. For cohort 1, safety analysis will occur at the end of chemoradiation. For patients in cohort 2 (who receive nivolumab following chemoradiation), evaluation for safety will occur 4 weeks following initiation of maintenance nivolumab. For patients in cohort 3, safety analyses will occur at the end of chemoradiation and after maintenance therapy has completed.

Criteria that will determine safety will include:

- Grade 3 or higher adverse events that persists for 14 days or longer despite dose-holds and/or maximal medical support. This excludes uncomplicated neutropenia and any laboratory abnormalities deemed by the treating clinician as having no clinical significance
- Inability to complete chemoradiation within 8 weeks

The BrUOG overall PI, the Women & Infants' Hospital site PI (once study is activated), and the Medical Director of BrUOG will review safety data as described to make determinations of feasibility. Enrollment to cohort 2 will not be dependent on the safety review for cohort 1. However, the safety review will be completed for cohort 2, before enrollment begins in cohort 3.

If more than 25% of patients (more than 2 patients in cohort 1 or more than 1 patient in cohort 2) experience a grade 3 or higher adverse event that persists for 14 days or longer, despite dose-holds and/or maximal support, the treatment will be considered not feasible and the next cohort will not be opened.

If more than 25% of patients (more than 2 patients in cohort 1 or more than 1 patient in cohort 2) are unable to complete chemoradiation within 8 weeks, the treatment will be considered not feasible and the next cohort will not be opened.

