16.4 Analysis of Primary Endpoints

Time-to-event endpoint of progression free survival at 3 years will be described using the method of Kaplan-Meier, and presented with 90% confidence intervals. Patients that are alive without disease progression at time of analysis are censored at the date of last disease evaluation. Acute Treatment-related toxicities that occur during and within six months of study treatment will be summarized by maximum grade and by term using CTCAE v4.0 and reported with 90% binomial exact confidence intervals. Acute toxicities will be used to determine the feasibility within each cohort.

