16.6 Reporting and Exclusions

Evaluation of Toxicity

All participants will be evaluable for toxicity from the time of their first treatment.

Evaluation of the Primary Efficacy Endpoint

All of the participants who met the eligibility criteria and who receive at least one dose of study drug will be included in the main intent-to-treat analysis of the response rate.

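### Early withdrawers may be replaced with no exception for toxicity, and the plan does not say how they score on the feasibility criteria, so a cohort at its limit can move to feasible

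*Combined protocol and SAP*

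**What the plan says.** Section 16.2 plans 8 patients in cohort 1, 4 in cohort 2 and up to 12 in cohort 3, "to enroll a maximum of 24 evaluable patients in the trial". It allows the total to change for "replacement of participants who withdraw prior to completion of the third week of chemoradiation, as these are the only reasons for replacement". No cause of withdrawal is named or excepted. The same section has all patients who begin therapy "included in the evaluation of toxicity for 30 days post last treatment, unless patient withdraws from study". Section 16.6 has no such exception: "All participants will be evaluable for toxicity from the time of their first treatment". Section 16.4 adds: "Acute toxicities will be used to determine the feasibility within each cohort".

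Section 16.1.1 sets two criteria: a grade 3 or higher adverse event lasting at least 14 days despite management, and "Inability to complete chemoradiation within 8 weeks". Each has the same limit: "If more than 25% of patients (more than 2 patients in cohort 1 or more than 1 patient in cohort 2") meet it, treatment is not feasible and the next cohort stays closed. The section also says: "Enrollment to cohort 2 will not be dependent on the safety review for cohort 1". Cohort 2 must be reviewed before cohort 3 enrolls, and section 5.4 opens cohort 3 only once safety is confirmed in cohorts 1 and 2.

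Neither *withdraw* nor *evaluable* is defined for this rule. Section 7.2 lists a participant's decision to withdraw separately from unacceptable adverse events, and section 7.3 speaks of patients removed for toxicity.

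**The concern.** The replacement window covers two induction doses of nivolumab and the first three weeks of chemoradiation, a period in which a participant may well leave because she tolerates treatment poorly. If she is replaced and not counted, the cohort loses a patient who bears directly on feasibility and gains one who may not. The error then runs only one way, toward feasible.

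The plan leaves the matter open on both criteria. On adverse events, 16.6 read with 16.4 points to keeping her, while 16.2 can be read as dropping her. On the 8-week criterion no section says whether she is a failure, a non-failure or outside the count. The cap of 24 evaluable patients, with the total allowed to grow for replacements, suggests without saying so that replaced patients fall outside the 8 and the 4 for which the limits are written. Two people could score the same data differently.

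At stake is the opening of cohort 3, about 12 patients given nivolumab both during and after chemoradiation. Cohort 2 bears on it through 16.1.1, and cohort 1 through section 5.4.

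**Working it through.** **The plan's own limits.** 0.25 × 8 = 2 and 0.25 × 4 = 1, so *more than 25%* means at least 3 of 8 (37.5%) or at least 2 of 4 (50%). 8 + 4 + 12 = 24. Both agree with 16.1.1 and 16.2.

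**Status of a replaced patient on the 8-week criterion.** External beam is given in 5 fractions a week (section 5.7). By the end of week 3 she has had at most 3 × 5 = 15 of 25 fractions, or 15 of 28 with a simultaneous integrated boost (section 5.7.5). Brachytherapy in general starts in the fourth week (section 5.7.5). Chemoradiation is therefore unfinished whenever she leaves within the window.

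**Effect of one uncounted failure, with an event-free replacement.**

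- Cohort 1: 3/9 = 33.3% (count 3, not feasible) becomes 2/8 = 25% (feasible).
- Cohort 2: 2/5 = 40% (count 2, not feasible) becomes 1/4 = 25% (feasible).
- Away from the limit the verdict can stand: in cohort 1, 4/9 becomes 3/8 = 37.5%, still not feasible.

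**Probability of a feasible verdict, 8-week criterion alone.** The plan gives no rates, so two are assumed: w, the chance that a dosed patient withdraws early because of toxicity (2-10%), and f, the chance that a retained patient fails (10%). The limit is c = 2 with n = 8, or c = 1 with n = 4.

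- A, withdrawers not counted: P(X ≤ c), X ~ Bin(n, f).
- B, withdrawers scored within the planned n: P(Y ≤ c), Y ~ Bin(n, p), p = 1 − (1 − w)(1 − f).
- C, withdrawers scored in addition to their replacements, limit fixed: P(K + X ≤ c), where K, the withdrawals before n patients are retained, is negative binomial with parameters n and 1 − w.

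Example, cohort 1, f = 0.10. A: 0.9^8 + 8(0.1)(0.9^7) + 28(0.01)(0.9^6) = 0.4305 + 0.3826 + 0.1488 = 0.962. B with w = 0.10: p = 1 − 0.9 × 0.9 = 0.19, giving 0.1853 + 0.3477 + 0.2855 = 0.819.

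| Cohort | w | A | B | A − B (points) | C | A − C (points) |
|---|---|---|---|---|---|---|
| 1 | 2% | 96.2% | 94.2% | 2.0 | 93.4% | 2.8 |
| 1 | 5% | 96.2% | 90.3% | 5.9 | 88.0% | 8.2 |
| 1 | 10% | 96.2% | 81.9% | 14.3 | 76.1% | 20.1 |
| 2 | 2% | 94.8% | 92.9% | 1.9 | 92.3% | 2.5 |
| 2 | 5% | 94.8% | 89.7% | 5.1 | 87.9% | 6.9 |
| 2 | 10% | 94.8% | 83.4% | 11.3 | 79.4% | 15.4 |

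A − B isolates the effect of not counting. C also enrolls extra patients under an unchanged limit; at w = f = 10% that accounts for about 6 of the 20 points in cohort 1 and 4 of the 15 in cohort 2.

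**Count against percentage.** If withdrawers are kept and replacements added, the printed counts and the 25% rule first disagree after 4 replacements: 3/12 = 25% and 2/8 = 25% pass a percentage rule but exceed the counts.

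**The case against.** Three points on the other side carry weight.

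First, a reader might infer that every early exit for toxicity is replaced. The documents do not support that. Many such exits are removals by protocol rule: discontinuation of nivolumab (5.5.1), radiation held for 7 days or longer (5.7.3, 6.2), grade 3-4 neurotoxicity (6.1, 7.1.4). Sections 7.2 and 7.3 word removal apart from withdrawal. What remains is the participant who chooses to leave because of tolerability; 16.2 does cover her.

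Second, a reader might infer a flat contradiction between 16.2 and 16.6. A softer reading is available: the clause in 16.2 is attached to the 30-day window, and sections 8.5 and 8.7 end reporting at withdrawal of consent, so it may mean only that collection stops. That reading would reconcile the two sections on adverse events. It gives no score on the 8-week criterion.

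Third, the verdict is not mechanical. Section 16.1.1 gives the decision to the overall principal investigator, a site principal investigator and the group's medical director, and the monitoring board (section 15) reviews all adverse events. People may notice a dropped patient, but neither section tells them how to score her.

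It is also fair that w and f have no support in the documents, and that a patient who leaves the study may still finish standard chemoradiation on time: 5.7.3 and 6.1 foresee continued treatment off protocol, and 5.5.1 has total treatment collected when nivolumab is discontinued. Scoring every toxicity exit as a failure would go too far.

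**Conclusion.** The concern stands as a gap in the go/no-go rule. The replacement provision has no exception for toxicity, the toxicity clause in 16.2 is ambiguous against 16.6, and 16.1.1 has no score for a withdrawn and replaced patient. If a patient who met a failure criterion is left out, the bias is toward feasible.

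The verdict changes only when the count is at its limit and the replacement has no event. Under the assumed 2-10% withdrawal and 10% other failure, leaving withdrawers out raises the chance of a feasible verdict by about 2 to 14 points in cohort 1 and 2 to 11 in cohort 2. The larger figures, 3 to 20 and 3 to 15, apply only if withdrawers are scored on top of their replacements. A reader might attribute the whole 20 points to non-counting; part of it comes from the extra enrollment. All these figures are illustrations for one criterion and not estimates for this trial.

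The plan should be corrected, because the rule governs the study's main decision and the limits are small enough for one patient to settle it.

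**What to change.** 1. In 16.1.1 and 16.2, state that every patient who receives protocol treatment, whether replaced, withdrawn or removed, stays in both feasibility counts with data up to the end of collection, and that replacement does not erase an event. Define *withdraw*, as distinct from *removed*, and *evaluable*.
2. Reword the exception in 16.2 to say that adverse-event collection ends when consent is withdrawn and that data up to then are included.
3. For the 8-week criterion, count a patient who withdraws or is removed because of toxicity as not completed, unless collected data show that chemoradiation was completed within 8 weeks. List exits for other documented reasons separately, show the result with and without them, and name in advance which result governs.
4. State that the printed limits (more than 2, more than 1) apply however many patients are dosed.

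The cost is wording. Section 7.2 already requires the reason for leaving protocol therapy on the case report form, which must separate toxicity from other reasons for withdrawal. The downside is a somewhat stricter gate, so cohort 3 is less likely to open.

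A separate, minor correction: 16.6 defines the primary efficacy set for the response rate, while the efficacy endpoint in 1.2.3 and 16.4 is progression-free survival. Align 16.6 with it.

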- Cohort TWO: Chemoradiation followed by Nivolumab maintenance for 2 years (total, four patients)
 - o Patients will proceed with definitive chemoradiation alone.
 - o 2-3 weeks following completion, patients will begin Nivolumab 480 mg IV every 4 weeks (+/- 3 days) for a planned duration of 2 years.
- Cohort THREE: Nivolumab 240mg IV during chemoradiation and then as nivolumab monotherapy 480mg IV (beginning no more than 4 weeks post CRT) for 2 years (total, approximately 12 patients to enroll allow for total study)

BrUOG 355: 7/8/17, 7/11/17, 7/20/17, 8/7/17, 8/8/17, 8/14/17, 8/16/17, 8/21/17, 8/22/17, 8/24/17, 8/28/17, 9/5/17, 9/6/17, 9/8/17, 9/11/17, 11/7/17, 11/8/17, 11/19/17 approved DD, 11/20/17, 12/12/17, 12/14/17, 1/29/18, 2/1/18, 2/6/18, 2/7/18, 2/8/18, 2/9/18, 2/12/18, 2/13/18, 3/8/18 all reviews, 3/9/18, 3/13/18, 3/14/18, 3/15/18, 4/19/18, 4/23/18, 5/29/18, 6/5/18, Amendment # 1 7/9/18, Amendment # 2 12/12/18, Amendment #3, 4/6/2020, Amendment #4 5/11/2020

enrollment of up to total 24 patients on study)

- Patients will receive nivolumab during definitive chemoradiation (as in cohort one) followed by nivolumab alone (as in cohort two). Pending safety data of cohort one, patients may be stratified by the radiation field, as in cohort One.

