5.6 Definitive Chemoradiation Plan

Standard therapy guidelines for definitive chemoradiation in cervical cancer will be utilized during this trial. All patients will receive tailored pelvic (if para-aortic nodes are negative) and/or extended field, pelvis+para-aortic, radiation therapy (if para-aortic nodes are involved) with a plan for daily delivery of RT (Monday-Friday) for approximately 6 weeks (which may include brachytherapy).

Cisplatin:

40 mg/m² of cisplatin (maximum total dose of 70 mg/week and maximum BSA=1.75m²)

Dosing on Days: 1, 8, 15, 22, 29, 36 (preferably on Mondays or Tuesdays). The only exception allowed is to account for holidays or unexpected events that warrant closure of the radiation oncology or infusion center, in which case treatment is allowed within the next fully operational day. For example, if D8 falls on a holiday, treatment with cisplatin (and with nivolumab if scheduled) should occur on next day, which will be counted as D8 with all subsequent days rescheduled to allow for a 7-day interval between dosing.

- Cisplatin should be infused **over approximately 1 hour**, beginning on day 1 of radiation therapy.

One hour before cisplatin administration, 500-1000 ml of normal saline should be infused intravenously, as per institutional standard of care.

Appropriate antiemetics should be administered prior to cisplatin. Additional fluid may be given as needed for symptomatic support. Premedications for nausea and vomiting prophylaxis should follow institutional guidelines.

Immediately after completion of the cisplatin infusion, an additional 500-1000 ml normal saline should be infused over one hour. It is highly recommended that KCl 20-40 meq and MgSO₄ 2 grams be added to the normal saline in the post hydration fluid given that hypomagnesemia and

BrUOG 355: 7/8/17, 7/11/17, 7/20/17, 8/7/17, 8/8/17, 8/14/17, 8/16/17, 8/21/17, 8/22/17, 8/24/17, 8/28/17, 9/5/17, 9/6/17, 9/8/17, 9/11/17, 11/7/17, 11/8/17, 11/19/17 approved DD, 11/20/17, 12/12/17, 12/14/17, 1/29/18, 2/1/18, 2/6/18, 2/7/18, 2/8/18, 2/9/18, 2/12/18, 2/13/18, 3/8/18 all reviews, 3/9/18, 3/13/18, 3/14/18, 3/15/18, 4/19/18, 4/23/18, 5/29/18, 6/5/18, Amendment # 1 7/9/18, Amendment # 2 12/12/18, Amendment #3, 4/6/2020, Amendment #4 5/11/2020

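### Replacement stops at week 3 of chemoradiation, so the cohort 2 safety gate to cohort 3 may rest on 2 or 3 patients exposed to maintenance nivolumab instead of 4

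*Combined protocol and SAP*

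**What the plan says.** **Replacement.** Section 16.2 has one rule for all cohorts. It allows "replacement of participants who withdraw prior to completion of the third week of chemoradiation, as these are the only reasons for replacement". The planned size is 8 in cohort 1, then "4 in cohort 2, and up to 12 in cohort 3 to enroll a maximum of 24 evaluable patients in the trial".

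**Cohort 2 treatment.** After two induction doses of nivolumab, section 5.4 states: "Patients will proceed with definitive chemoradiation alone". Maintenance comes later: "2-3 weeks following completion, patients will begin Nivolumab 480 mg IV every 4 weeks". Section 5.6 plans "daily delivery of RT (Monday-Friday) for approximately 6 weeks".

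**Cohort 2 gate.** Under section 16.1.1, "evaluation for safety will occur 4 weeks following initiation of maintenance nivolumab" in this cohort, and "the safety review will be completed for cohort 2, before enrollment begins in cohort 3". Section 5.4 adds that cohort 3 opens once safety has been confirmed in the first two cohorts.

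**Threshold.** There are two failure criteria: a grade 3 or higher event lasting 14 days or more despite dose holds or support, and chemoradiation not completed within 8 weeks. For each, the regimen is not feasible if over 25% of patients fail, which section 16.1.1 translates as more than 2 patients in cohort 1 and more than 1 in cohort 2.

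**Who counts.** Section 16.2 includes everyone who begins protocol therapy in the toxicity evaluation, except those who withdraw from study. Section 16.6 counts all participants from first treatment. Neither section says who is evaluable for the cohort 2 review or how many patients must have received maintenance.

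**The concern.** The replacement window suits cohort 1, where the question is tolerance of nivolumab during chemoradiation. Cohort 2 asks about maintenance, which has not begun when the window closes.

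The protocol provides several ways to leave between week 3 and the first maintenance dose without meeting either failure criterion:

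- Persistent renal impairment stops nivolumab while chemoradiation continues off protocol (section 6.1). She may finish within 8 weeks and have no qualifying adverse event.
- A radiotherapy delay of 7 days or more means removal, with further chemoradiation left to the physician (section 5.7.3).
- A related grade 3/4 event can end nivolumab (section 5.5.1) and still resolve in under 14 days.
- She may progress or decline further treatment (section 7.2).

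Such a patient tells us nothing about maintenance and is not replaced.

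This matters because cohort 2 supplies the only planned maintenance review before cohort 3 enrols. Cohort 3's own reviews fall at the end of chemoradiation and after its 2 years of maintenance, whereas accrual to the whole trial is planned at about 9 months. Cohort 3 is up to half of the trial and combines concurrent and maintenance nivolumab.

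**Working it through.** **1. The plan's own figures.** 25% x 4 = 1, so the cohort 2 rule trips at 2 failures. 25% x 8 = 2, so cohort 1 trips at 3. 8 + 4 + 12 = 24. All agree with the text. The translation into more than 1 patient is exact only when the denominator is 4.

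**2. Length of the uncovered gap.** Inputs: chemoradiation about 6 weeks (section 5.6), maintenance 2-3 weeks later (5.4), evaluation 4 weeks after that (16.1.1).

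- End of week 3 to first maintenance dose: (6 - 3) + 2 = 5 to (6 - 3) + 3 = 6 weeks.
- If chemoradiation takes the full 8 weeks: 7 to 8 weeks.
- End of week 3 to the evaluation: 5 + 4 = 9 to 8 + 4 = 12 weeks.

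**3. How often places are lost.** The documents give no attrition figure. Let d be the chance that a patient leaves in the gap, assumed 5-30% and independent between patients. P(at least 1 of 4) = 1 - (1 - d)^4, and P(at least 2) = 1 - (1 - d)^4 - 4d(1 - d)^3.

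| Assumed d | At least 1 lost | At least 2 lost | At least 3 lost |
|---|---|---|---|
| 5% | 18.5% | 1.4% | 0.05% |
| 10% | 34.4% | 5.2% | 0.4% |
| 20% | 59.0% | 18.1% | 2.7% |
| 30% | 76.0% | 34.8% | 8.4% |

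**4. What the gate can detect.** Let m be the number who start maintenance and p the true rate of qualifying events arising in that period (assumed; not in the documents). Leavers are taken to contribute no failure.

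- Fixed count (2 failures needed): 1 - (1 - p)^m - mp(1 - p)^(m-1).
- Percentage on exposed patients only: with m = 3 or 2, one failure is 33% or 50% and trips the rule, so 1 - (1 - p)^m.

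| m exposed | Fixed count, p = 25% | Fixed count, p = 40% | Fixed count, p = 50% | Percentage, p = 40% |
|---|---|---|---|---|
| 4 | 26.2% | 52.5% | 68.8% | 52.5% |
| 3 | 15.6% | 35.2% | 50.0% | 1 - 0.6^3 = 78.4% |
| 2 | 6.3% | 16.0% | 25.0% | 1 - 0.6^2 = 64.0% |

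The stricter reading has its own cost. At a true rate of 10%, the rule trips 5.2% of the time with 4 exposed, but 1 - 0.9^3 = 27.1% with 3 and 1 - 0.9^2 = 19.0% with 2.

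**5. Averaged over attrition.** Under the fixed count and p = 40%, the overall chance of tripping the rule is 49%, 45%, 38% and 31% at d = 5%, 10%, 20% and 30%, against 52% with no losses.

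**6. Precision.** With no events, the upper limit of the exact 90% interval (the level used in section 16.4) is 1 - 0.05^(1/m): 53% for m = 4, 63% for m = 3, 78% for m = 2.

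**The case against.** A reader might infer that cohort 2 could pass and cohort 3 open with nobody having received maintenance. The text does not support that. The review is timed from the start of maintenance, so with no starters it could not be held as defined, and section 5.4 requires safety to be confirmed. The case is also remote: losing all four has probability under 1% even at 30% attrition.

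A second tempting reading is that leavers always stay in the denominator, so losses always weaken the rule. Section 16.2 exempts patients who withdraw from study, and the rule is worded first as a percentage. On that reading losses make the gate stricter. What stands is that the text does not decide between the two readings, and they move the result in opposite directions.

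Third, some exits are failures themselves: an event lasting 14 days or more, or chemoradiation not completed within 8 weeks. Two failures on the same criterion close the gate, and neither criterion is confined to maintenance. The uncovered group is therefore narrower than all leavers, and step 4 applies to that narrower group.

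Fourth, three named roles judge feasibility and the DSMB reviews cumulative toxicity (section 15), so cohort 3 does not open automatically. They could ask for more patients, but nothing requires it.

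Finally, this is a feasibility pilot. Failure to reach maintenance is a finding in its own right, and four patients give weak detection at best. Both points are fair. They argue for reporting such losses, not for letting them reduce an already small gate.

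**Conclusion.** The concern holds in a limited form. The stated replacement rule ends 5-6 weeks before the exposure that cohort 2 is meant to test, and no minimum number exposed is set. The realistic consequence is a gate resting on 2 or 3 patients, with an unclear denominator. At an assumed 40% event rate, 3 exposed patients give a 35% or a 78% chance of tripping the rule depending on the reading, and 2 give 16% or 64%, against 52% with all four. How often this arises depends on attrition, which the documents do not give: one or more unexposed in 19%, 34%, 59% or 76% of trials, and two or more in 1%, 5%, 18% or 35%, at 5%, 10%, 20% or 30%. The event rate and independence between patients are also assumptions. The mismatch between replacement window and review, and the unsettled denominator, rest on the text alone. It should be corrected before cohort 3 opens.

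**What to change.** In sections 16.1.1 and 16.2:

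- Define a cohort 2 patient as evaluable for the maintenance review if she received at least one maintenance dose and was observed for 4 weeks, or left earlier because of an event meeting a section 16.1.1 criterion. The latter counts as a failure.
- Complete the cohort 2 review, and open cohort 3, only when 4 patients are evaluable.
- Apply the more-than-1-of-4 count to those 4, which makes the count and the percentage agree.
- Fill vacant places from the cohort 3 remainder, so the total stays 24.
- Keep every treated patient in the toxicity and 8-week chemoradiation assessments, and report failure to reach maintenance as a feasibility result.

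This holds the chance of tripping the rule at 52% for a 40% event rate, whatever the attrition. Expected cohort 2 enrolment is 4/(1 - d): 4.2, 4.4, 5.0 or 5.7 patients at 5%, 10%, 20% or 30%.

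The cost is wording, one or two fewer patients in cohort 3, and a possible delay to its opening. A replacement enrolled only after the loss is known needs roughly 2 + 2 weeks for induction and the interval to chemoradiation, 6 for chemoradiation, 2-3 to maintenance and 4 of observation, or 16-17 weeks. No dose or treatment rule changes.
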